That human migraine can be treated effectively with episodic injections of anti-CGRP antibodies begets the question whether these newly prescribe-able medications can be repurposed for other trigeminal pain conditions and the related glossopharyngeal cranial nerve pain which are known to involve neurogenic inflammation. Another pain condition with poor treatment options for sufferers is fibromyalgia, especially fibromyalgia with associated small fiber neuropathy which leads to systemic de-afferentiation of patients' sensory system. In this condition, there is strong evidence for presence of neurogenic inflammation, and it is a rational concept that neurogenic inflammation contributes to disease pathogenesis and especially to the dominating clinical symptom of pain.

We propose to treat patients (targeting enrollment of n=20) who suffer from trigeminal or glossopharyngeal nerve pain in the context of painful small fiber neuropathy. We predict that recruitment of these patients will not be a challenge in the PI's clinics, based on previous experience and ongoing referral practice. Primary criterion is to establish an excellent safety profile that recapitulates the favorable data recorded in migraineurs. The primary pain-related objective is reduction of pain and reduced use of rescue and other anti-pain medications.

Secondary pain-related objectives are improvement of circadian rhythm impairment by galcanezumab, improvement of serum markers for chronic inflammation including protein/peptide as well as small non-coding RNA molecules, and discovery of DNA polymorphisms that predispose treated patients to accentuated responses of either lack of response or particularly potent response.

Clinical Collaborators

[name] MD, Duke Neurology
[name] MD

Hypothesis/ Purpose

We hypothesize that the proposed galcanezumab regimen will be found safe in our patient population, and that provisional evidence of its effectiveness will become apparent. We envision galcanezumab to target neurogenic inflammation in the trigeminal territory and neurogenic inflammation associated with small fiber neuropathy/fibromyalgia.

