Before treatment, there will be a 4 week observation-only period, and another one 8 weeks post-treatment, so that the total study period will be 6 months.

We aim for 20 patients to be included in this study.

see more detailed graphics in the next section

In terms of ancillary, laboratory-based studies, we intend to draw blood before treatment and at the 45-, 75-, 105- and 135-day of treatment time-points. We will measure cytokine/chemokine/lipid pain- and inflammation markers in patients' serum, also determine microRNA in their serum, and genomic DNA polymorphisms, the latter only at baseline. Please see next section for more detail.

To establish safety of the anti-CGRP treatment in this patient cohort, blood draw at baseline and at the 45-, 75-, 105- and 135-days of treatment time-points will also include routine systemic sentinel/surveillance markers, namely comprehensive metabolic panel and complete blood count with differential, and complete urinalysis. No more than 45 ml of blood will be collected at any given visit.

In terms of additional safety parameters, we propose an open, patient-kept side-effect log, plus home-based recordings of blood pressure, heart rate and weight at a frequency of 2x/week.

We will set up a data and safety monitoring board for proper management and oversight of data handling and patient safety-related issue; see next section.

[figure not shown]
We expect to observe effective treatment, at least in a significant subgroup of patients. Effectiveness of treatment, also magnitude of any observed therapeutic effect will be correlated with the pain/inflammation proteinaceous, lipid and RNA-based biomarkers in patients' serum, also with any polymorphisms in the patients' genomic DNA.

We also expect galcanezumab treatment to show another record of safe treatment, our expectation sculpted by analysis of in-depth data from treatment of migraineurs. Yet we will remain vigilant and implement the proposed safety sentinel measures in order not to miss adverse effects. This appears prudent because trigeminal or glossopharyngeal nerve pain plus small-fiber neuropathy is a different underlying disorder than migraine, likely representing a higher prevalence in peri-menopausal female patients. We also believe it is likely that level of chronic pain suffering-associated stress will be higher in our study population than in migraineurs.

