We also expect that the proposed studies will be very important for guiding future, more in-depth studies involving larger patient cohorts, placebo-controlled/double-blinded studies, which will possibly lead us toward a personalized-medicine approach.

Study Design Detail

1) Schedule of Activities over Time

2) Blood draw: detailed analysis

Before treatment, and at 45th, 75th, 105th and 135th day of treatment, we propose to assess the following blood parameters, related to pain-associated biomarkers in the systemic circulation.

For this, we propose to study cytokine/chemokine pain- and inflammation markers in patients' serum, using commercially available protein multiplex detection assays. In serum, the following 39 cytokines/chemokines/lipid mediators/peptides will be measured: EPO, GM-CSF, IFN- γ , IL-1 β , IL-2, IL-4, IL-5, IL-6, IL-9, IL-10, IL-12/IL-23p40, IL-12p70, IL-13, IL-15, IL-16, IL-17A, IL-17A/F, IL-17C, IL-17E/IL-25, IL-17F, IL-21, IL-22, IL-23, IL-27p28/IL-30, IL-31, IL-33, IP-10, KC/GRO, MCP-1, MIP-1 α , MIP-1 β , MIP-2, MIP-3 α , TNF- α , VEGF-A, TGF- β , CGRP, Resolvin-D1, Prostaglandin-E2. For these measurements, we will be using a human 35-plex ELISA (U-PLEX Biomarkers) and single ELISAs (Signosis; Cayman).

These are key mediators and indicators of pain and inflammation. We believe it will be feasible to conduct these assays. For each marker there is sufficient evidence supporting its role in pro-algesic inflammation or organismal response to tissue damage. We are

convinced that their ensemble will prove a powerful source of mechanistic data that will elucidate treatment responses to galcanezumab in our patient population.

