In addition, we propose to detect systemic circulatory microRNAs. These molecules will be identified by RNA-seq starting with small RNA-preparation from patients' serum. This approach is preferred over a candidate approach since it is maximally unbiased. We believe that an unbiased approach will be more suitable because pain-associated circulatory miRNA markers are not firmly established, therefore a "candidate approach" is not even feasible. With an open, unbiased discovery approach of miRNAseq we minimize the risk to miss anything of relevance. The number of miRNAs is considered currently slightly >2000, thus very roughly 1/10 of the number of all protein-coding genes. MicroRNAs have been established robustly as biomarkers in specific malignancies, also with chronic inflammation, so that a tentative association with specific pain conditions appears an appealing opportunity to make these discoveries in our patient population.

Baseline blood draw (and only at that time point because it will not change through treatment) will also include preparation of genomic DNA from white blood cells to sequence the patients' genomic DNA whole-exome. Having these data available will position us favorably so that we can identify any genetic abnormalities (e.g. in pain-associated voltage-gated sodium channels, pain-TRP channels, inflammation-associated genes) in our patients. First we will be analyzing the genomic DNA profile for presence of pain susceptibility genes in known genes and their respective families, such as voltage-gated sodium channels, neurogenic inflammation pathway, opioid receptor signaling, MRGPR-X related pathway, pain-TRPs and associated proteins, β -adrenergic signaling, COMT pathways, algogenic lipid mediator pathways, and more. After identification of particular high-responders and low/non-responders, we will try to identify association of these particular response patterns with any measured biomarker, including DNA polymorphisms, miRNA, lipid, protein/peptide markers.

3) Data Safety Monitoring Board (DSMB)

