Patients will be recruited via the PI's clinics at Duke University, the Duke Clinics that typically refer to her attention and outside clinics and providers that refer to her as well, and DEDUCE database. In case of slow recruitment patient self-help and patient advocacy associations in the facial pain arena will be informed of the ongoing study to assist with recruitment. These organizations (Facial Pain Research Foundations, Facial Pain Association) are well-known to the PI.

11) Brief Statistical Analysis Plan

Only patients who complete the study will be included in the statistical analysis.

Response to treatment will be assessed by comparing pain metrics during the 90-day treatment period vs averaged 30 day "run-in". Outcome variables will consist of selected readout parameters of "pain metrics", namely pain subjective rating on VAS (0-10) and medication co-use. Additional outcome variables include circadian rhythm-associated metrics. A daily readout for each variable will be entered into their log by each patient, or by automatic activity reads from their motion tracking device. In similar manner, we will compare pain metrics during the 90-day treatment period vs 60-day post-treatment observation.

We intend to conduct the study with an n=20 patients to successfully complete the study. This selected number appears the most feasible and practicable number. We are confident that with an n=20 we will be in a position to do justice to the objective of initial assessment of the safety of galcanezumab in the condition under study, trigeminal or glossopharyngeal pain in the context of painful small fiber neuropathy/fibromyalgia.

Following completion of the study, we will have estimates of effect sizes and corresponding 95% confidence intervals providing information on the precision of the statistical estimates of treatment effect. Power analysis will be performed based on these estimates and will provide us with guidance for sample sizes of follow-up studies that aim for demonstrating effectiveness.

The statistical analysis will be based on a linear mixed model for repeated measures. The

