time course of pain metrics reported during the treatment period will be compared with metrics during the run-in baseline. The covariance matrix describing the nature of correlations between repeated measures will be selected based on Akaike information criterion and Bayesian information criterion, as guided by our statistics software, SAS/STAT15.1. p-values <0.05 will be considered statistically significant. Effects of treatments will be investigated with the introduction of treatment as a binary covariate (we will evaluate the effects of pre- and post-treatment in two different models).

Patients' anti-pain treatment response will be correlated with blood markers for pain, inflammation and miRNA, and also for genomic markers. This approach will be pursued in order to identify candidate biomarkers that pre-dispose patients to experience an effective or non-effective treatment response. In case of recording any particular safety-related parameters, correlation of these markers to safety metrics will also be conducted. Association between molecular biomarkers and pain- and activity-related metrics will be evaluated (i) at each time point separately using a linear regression model; (ii) by modeling the association across all time points and including time covariate in the linear regression model. The ensemble of these approaches will help determine the periods when pain or activity-related metrics and molecular markers co-evolve and become highly correlated.

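### Improvement of serum markers is a secondary objective, but section 11 uses the markers only in association analyses and never estimates whether any marker changes on treatment

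*Combined protocol and SAP*

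**What the plan says.** **Objective.** The Abstract lists, among the secondary objectives, "improvement of serum markers for chronic inflammation including protein/peptide as well as small non-coding RNA molecules".

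**Data.** Study Design / Overview states: "we intend to draw blood before treatment and at the 45-, 75-, 105- and 135-day of treatment time-points". Under 2) Blood draw: detailed analysis, "the following 39 cytokines/chemokines/lipid mediators/peptides will be measured". Serum miRNA is to be found by sequencing rather than from a candidate list, and of the size of that field the section says "The number of miRNAs is considered currently slightly >2000".

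**Analysis.** Section 11 gives two lists of outcomes. The first begins "Outcome variables will consist of selected readout parameters" and names the pain rating and medication co-use. The second reads "Additional outcome variables include circadian rhythm-associated metrics". Serum markers are in neither. The comparison of treatment with run-in is stated for pain: "time course of pain metrics reported during the treatment period will be compared with metrics during the run-in baseline".

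Markers enter section 11 in three places:
- correlation of the pain response with blood and genomic markers, to find candidate predictors of response;
- correlation of markers with safety metrics, if safety findings are recorded;
- regression, introduced by "Association between molecular biomarkers and pain- and activity-related metrics will be evaluated", first at each time point and then across time points with time as a covariate.

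One threshold, p<0.05, is given for the whole plan. No multiplicity adjustment is mentioned.

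**The concern.** Improvement of a marker means that its level moves, in a favourable direction, from the pre-treatment value. That is a within-patient change. The planned marker analyses estimate something else: whether patients or visits with higher marker values also have more pain, less activity or more safety findings. A marker can fall in every patient and be unrelated to pain, or track pain closely and not move on average.

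If the plan is followed as written, up to five draws in each of 20 patients are assayed for 39 markers and sequenced for miRNA, and a stated secondary objective still has no estimate. There are two practical risks. A marker-pain correlation may be reported as if it showed improvement. Or a change analysis may be added after the data are seen, with a free choice of draws, markers and direction, and with the general p<0.05 rule applied to a very large number of tests.

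**Working it through.** The plan gives no effect size, SD or power for any marker, and 20 is described as a feasibility number. There is therefore no figure of the plan's own to reproduce. The check has a textual part and an arithmetical part.

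**1. Each place that uses markers, set against the objective**

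| Place | Role of the marker | Estimates change from baseline? |
|---|---|---|
| Study Design / Overview | correlated with size of treatment effect | no |
| 2) Blood draw | associated with high and low/non-response | no |
| Section 11, outcome lists | absent | no |
| Section 11, mixed-model comparison with run-in | stated for pain metrics | no |
| Section 11, response and safety correlations | correlated | no |
| Section 11, regression at each time point | association within one draw | no |
| Section 11, regression across time points | association, with a time covariate | not as specified |

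The last row is the closest the plan comes. If the marker were the response, the time coefficient would be a marker trend adjusted for pain or activity. The text does not say which variable is the response, states the aim as finding when metrics and markers move together, names no treatment-versus-baseline contrast, and mentions no patient effect for the repeated draws.

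**2. Can association stand in for change?** Illustration under assumed values: n=20, marker SD 1, within-patient correlation 0.5, a true fall of 1 SD, no link to pain. The SD of the change is √(2×(1−0.5)) = 1. In 4000 simulated trials the marker-pain correlation at one post-baseline draw was significant at 0.05 in 5.1%, which is the false-positive rate. The paired comparison with baseline was significant in 98.9%.

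**3. What n=20 offers for a change estimate**
- 95% CI half-width, in SDs of the change: t(0.975, 19)/√20 = 2.093/4.472 = 0.47.
- Detectable change for a single comparison with the pre-treatment draw (noncentral t, two-sided, 80% power assumed): 0.66 SD at 0.05.
- With Bonferroni over the panel, 0.05/39 = 0.00128: 1.05 SD.

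**4. Cost of leaving the threshold unadjusted, if no marker changes**
- Panel: 39×0.05 = 1.95 expected false positives. The chance of at least one is 1−0.95^39 = 0.86 if the tests are independent.
- miRNA: 2000×0.05 = 100, if about 2000 are tested. The number detectable in serum is not given, and the count scales with it.

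**5. Which draws are on treatment?** Study Design / Overview and 2) Blood draw describe days 45, 75, 105 and 135 all as days of treatment. Study Design / Overview gives 12 weeks of treatment (84 days), and section 11 gives 90 days.
- Counted from first dose: days 45 and 75 are on treatment; 105 and 135 are after it.
- Counted from the start of a 30-day run-in, treatment spans days 30 to 120: days 45, 75 and 105 are on treatment; 135 is after it.

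Under neither count are all four draws on treatment.

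**The case against.** The strongest defence is that section 11 leaves room for a marker analysis. It says in general terms that the analysis rests on a repeated-measures mixed model, and the sentence introducing treatment as a binary covariate is not expressly limited to pain. Together with the time covariate in the across-time regression, a generous reader could find a marker trend there. So it would be too strong to infer that the plan ignores marker behaviour over time. But the generic sentences stand next to text about pain metrics, the outcome lists omit markers, and no marker contrast is written. The latitude is real; the analysis is not specified.

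A second defence is weight. The laboratory work is called ancillary, the trial is a small open-label pilot, section 11 is headed as brief, and the discovery aims are served by the association analyses. That stands, and it limits how serious the point is. Narrowing the objective to association would also remove the mismatch, but it would give up a question that the scheduled draws can address.

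Three stronger readings are tempting and not supported:
- That section 11 relates markers to pain alone. It also covers activity metrics and, conditionally, safety metrics.
- That a change contrast would show an effect caused by galcanezumab. The study has one arm, treatment is added to existing therapy, and nothing separates drug effect from time or co-medication.
- That the plan chose an unsuitable measurement scale for the markers. It names no scale.

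**Conclusion.** The point holds. A stated secondary objective has no planned analysis: the marker analyses that are specified target association, and none compares on-treatment levels with the pre-treatment level. This goes beyond missing detail, because following the text exactly yields a different quantity. It should be fixed, but it does not touch the primary safety or pain objectives.

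The precision figures (half-width 0.47 SD; detectable change 0.66 SD unadjusted, 1.05 SD at 0.05/39) assume 20 completers, a single paired comparison, roughly normal changes and, for the detectable values, 80% power. They are in SDs of the change, because the documents give no marker SDs from which to convert them to concentrations. The false-positive counts assume that no marker changes. The simulation shows only that a test of association can be blind to a real change; its effect size and correlation are assumed.

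**What to change.** 1. **Reconcile the draw days** with the 12-week and 90-day statements of the treatment period, state the day from which draws are counted, and class each draw as pre-treatment, on treatment or post-treatment.
2. **Panel of 39 markers.** Add to section 11, for each marker, a repeated-measures mixed model of log concentration with visit as a factor and a patient effect, treating values below the detection limit as censored. Report the mean of the on-treatment draws minus the pre-treatment draw, with a 95% CI.
3. **miRNA.** Use a paired count-based model suited to sequencing data, with the same contrast.
4. **Multiplicity.** Control the false discovery rate at 5%, separately within the panel and within miRNA, in place of unadjusted p<0.05.
5. **Claims.** State in advance, marker by marker, the direction that counts as improvement. Base any statement of improvement on this contrast only, and describe it as change on treatment in an uncontrolled single-arm study. Keep the association analyses for their stated discovery purpose.

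Cost: SAP wording and extra analysis work, mainly the censored models and a separate miRNA analysis, and fewer markers reaching significance than at an unadjusted 0.05. No new samples or patients.

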Treatment with a CGRP-neutralizing antibody, galcanezumab in this specific patient group, being seen in the PI's clinics on a regular basis, is rooted in the rationale of unmistakable presence of clinical signs of neurogenic inflammation in the painful territory, such as episodic swelling combined with redness/hyperemia, also relief by external cold application which typically patients with trigeminal or glossopharyngeal nerve pain abhor.

Primary Outcome Measures

Primary criterion is to establish an excellent safety profile that recapitulates the favorable data recorded in migraineurs. The primary pain-related objective is reduction of pain and reduced use of rescue and other anti-pain medication.

Inclusion Criteria

- G50.1 diagnosis (can encompass an add-on G50.0 and other headache G43.... codes), or G52.1 diagnosis code (with explicit mentioning of pain of glossopharyngeal origin) **AND** small fiber neuropathy diagnostic codes G63.3, G60.8, G62.8 (can encompass fibromyalgia diagnostic code M79.7)
- 18-80 years old
- not allergic to galcanezumab and other hu mAb biologics

Exclusion Criteria

- allergic to galcanezumab and other hu mAb biologics
- pregnancy

Study Design / Overview

We propose to treat patients open label for 12 weeks, with galcanezumab, supplied by Eli Lilly, as add-on to all other therapeutic measures. We propose to use a 240mg/120mg/120mg regime, with subcutaneous (self-)injections every 4 weeks.

To reflect pain experienced by patients, the primary read-out is pain level on a 0-10 visual analog scale. We will be prompting patients to record a daily summary read at the end of each day.

[figure not shown]
The second criterion is reduction of intake of anti-pain medication (rescue PRN or regular) which the patients will record.

Chronic pain, especially fibromyalgia pain combined with trigeminal or glossopharyngeal nerve pain, is a potent disruptor of circadian rhythm. We strongly believe that this is an important and hitherto under-appreciated contributor to individual disease burden. Therefore, the third criterion is assessment of circadian rhythm function. We will assess this by having the patient rate subjectively how energetic they feel during awake day-time. Wearable activity monitors will be used to address how many hours patients sleep per

24h period, with detailed focus on total duration of sleep/rest and duration of night-time sleep only.

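### The primary criterion promises a migraine-like safety conclusion that about 20 uncontrolled patients cannot support, and section 11 plans no safety estimate and no safety analysis set

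*Combined protocol and SAP*

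**What the plan says.** The Abstract and Primary Outcome Measures use the same sentence: "Primary criterion is to establish an excellent safety profile that recapitulates the favorable data recorded in migraineurs". Study Design / Overview also presents the laboratory panel as a means of establishing safety. Treatment is open label and added to existing therapy, with no control arm.

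Section 11 is more modest: "We are confident that with an n=20 we will be in a position to do justice to the objective of initial assessment of the safety". It justifies the number on practical grounds: "This selected number appears the most feasible and practicable number". The Abstract describes it as "targeting enrollment of n=20", whereas section 11 says "We intend to conduct the study with an n=20 patients to successfully complete the study".

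Section 11 has one analysis-set rule: "Only patients who complete the study will be included in the statistical analysis". Its effect sizes, 95% intervals and mixed model concern the treatment effect on pain and related metrics. Safety enters the analysis only as a correlation of biomarkers with safety metrics, to be run if any particular safety parameters are recorded.

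Elsewhere the protocol collects substantial safety data: blood and urine panels at baseline and days 45, 75, 105 and 135, a patient side-effect log, and blood pressure, heart rate and weight twice a week (Study Design / Overview). Section 7 has all AEs after consent recorded. It does not require investigators to look actively for AEs once the 90-day treatment period is complete.

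**The concern.** The primary criterion is worded as a conclusion to be reached. It also has a comparative part, "recapitulates the favorable data recorded in migraineurs", with nothing to compare against: the documents give no migraine AE or SAE rate, no margin, and no definition of what would count as success. Section 11 sets a softer aim, so a reader cannot tell which conclusion the study intends to draw.

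The outcome called primary also has no planned estimate. The statistical detail goes to pain, medication and circadian metrics. Whoever writes the report would have to choose the safety denominator, summary and observation window after seeing the data. The only denominator on offer is completers, which is the wrong one for tolerability because leaving the study can itself be the safety event.

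At stake is whether the main conclusion of the report can be supported by its data.

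**Working it through.** **Inputs.** N = 20, read either as enrolled (Abstract) or as completing (section 11). No dropout rate, reference rate or margin is given. N was chosen for feasibility, so there is no sample-size calculation to reproduce. All event rates below, and the alternatives of 25 treated or 18 and 16 completing, are assumptions.

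**1. What zero events would exclude.** The exact two-sided 95% upper limit for 0 of n is 1 − 0.025^(1/n); the one-sided limit is 1 − 0.05^(1/n).
- n = 20: 1 − 0.025^(1/20) = 16.8% (one-sided 13.9%)
- n = 25: 1 − 0.025^(1/25) = 13.7%
- n = 16: 1 − 0.025^(1/16) = 20.6%

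**2. How often zero events would be seen anyway.** P(0 of 20) = (1 − p)^20.
- p = 5%: 0.95^20 = 0.358, about 36%
- p = 10%: 0.90^20 = 0.122, about 12%, so at least one event appears 87.8% of the time

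**3. Precision when events occur** (Clopper-Pearson two-sided 95%, n = 20).
- 1/20: 0.1% to 24.9%
- 2/20: 1.2% to 31.7%
- 5/20: 8.7% to 49.1%

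**4. Matching a reference rate.** Take an assumed reference rate and the smallest count in 20 at which a one-sided exact test has alpha at most 0.05. Power to detect a true doubling is then:

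| Assumed reference | True rate | Reject at | Alpha | Power |
|---|---|---|---|---|
| 2% | 4% | 3 or more | 0.7% | 4.4% |
| 5% | 10% | 4 or more | 1.6% | 13.3% |
| 10% | 20% | 5 or more | 4.3% | 37.0% |
| 20% | 40% | 8 or more | 3.2% | 58.4% |

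Even a doubling would usually be missed at reference rates up to 10%, and would be missed about four times in ten at 20%. A non-significant difference would therefore say little about similarity to migraine patients.

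**5. What the completers rule would do if applied to safety.** As an illustration, suppose 20 are treated, two leave the study because of an AE, and 18 complete. In all treated patients, AE discontinuation is 2/20 = 10% (1.2% to 31.7%). In completers it is 0/18 = 0%, with an upper limit of 18.5%. The events disappear from the estimate because of how the denominator is defined. This assumes that those two patients count as non-completers; section 11 does not define completion.

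**The case against.** The protocol repeatedly limits its own claim. It calls itself a pilot and a phase 1b study, treats safety as a hypothesis, foresees larger placebo-controlled studies, and in section 11 says only that it will "do justice to the objective of initial assessment of the safety of galcanezumab in the condition under study". On that view the primary criterion is an aspiration. The softer aim is achievable: 20 patients can describe common effects, and the laboratory and vital-sign data suit that well. This part stands, and it favours wording the primary outcome descriptively too. It does not rescue the comparative claim.

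A reader might infer three stronger things, and the documents support none of them.
- *That a study with no serious events would be reported as having established safety.* No zero-event success rule or reporting rule appears, and Study Design / Overview commits to vigilance because the condition differs from migraine.
- *That patients harmed by treatment are removed from the safety evidence.* All AEs after consent go into the case report form. AEs causing discontinuation are followed up and the discontinuation is reported to the IRB (section 7). The monitoring board reviews cumulative AE data (section 3). The completers sentence governs the statistical analysis, and whether it is meant to reach safety is not said.
- *That section 11 ignores safety.* It names the aim and a conditional correlation with safety metrics. Neither is an incidence estimate.

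It would also be wrong to fix 16.8% as the study's limit. If section 11's target of 20 completers is met, 20 or more will be treated.

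**Conclusion.** The point holds in this form. The primary criterion asks for a safety conclusion and a match to migraine data that a single arm of about 20 cannot deliver and that has no stated benchmark. It also conflicts with the more modest aim in section 11. Section 11 specifies no AE or SAE incidence, no interval and no safety analysis set.

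On size, zero events would leave true rates up to 16.8% (20 treated) or 13.7% (25 treated, assumed) compatible with the data, and an assumed 5% rate gives no events in 20 about 36% of the time. The power figures depend on assumed reference rates because the documents supply none.

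The completers problem is conditional: it biases safety favourably only if the rule is applied to safety summaries, which the text neither says nor excludes. The sample size itself is not at fault for a pilot chosen on feasibility. The correction should be made before analysis, but it does not call for a change of design.

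**What to change.** 1. In the Abstract, Primary Outcome Measures and Study Design / Overview, restate the primary safety outcome as descriptive estimation of safety and tolerability. Label any comparison with migraine data as informal; otherwise name its source rate and margin.
2. In section 11, state that the completers rule does not apply to safety, and define the safety set as all patients given at least one injection.
3. For that set, report the number and percent with any AE, any SAE and any AE leading to discontinuation, each with an exact 95% interval. Add summaries of change in laboratory values and vital signs.
4. State the observation window for each summary. Section 7 does not require active AE seeking after the 90-day treatment period, so AE ascertainment may be less complete in the post-treatment period.
5. State what zero events would exclude for the number actually treated (16.8% for 20; 13.7% if it were 25), and say whether 20 means enrolled or completing.

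The cost is a weaker stated safety claim and one added table. The data for the treatment period are already being collected, and no extra patients are needed.
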